6.2 Details of Assessments

6.2.1 Clinical Assessment

Clinical assessment includes history, physical examination, weight and performance status. Participants will be reviewed by their study medical oncologist at Day 15, and at least 4 weekly during treatment and 6 weekly thereafter until radiological progression.

6.2.2 Standard of Care Imaging

CT chest, abdomen, and pelvis and ^{99m}Tc bone scan will be performed at screening, Day 99, then twelve weekly until radiological progression is demonstrated (unless radiological progression is documented prior).

6.2.3 Translational Imaging

^{68}Ga -PSMA and ^{18}F FDG PET/CT will be undertaken at screening prior to randomisation, and at first progression (Figure 4). Additional ^{68}Ga -PSMA PET/CT will be done at Days 15 and 92. All PET data will be analysed using MIM maestro software.

[figure not shown]

Figure 4. Translational components

6.2.4 Tissue Collection

Where available, archival formalin-fixed paraffin-embedded (FFPE) tumour tissue will be retrieved from all patients and may be used for translational research studies.

Additional tumour biopsy will be undertaken at baseline and at first progression in participants consenting to biopsies in the trial. This baseline biopsy will be guided by the screening ⁶⁸Ga-PSMA PET/CT result. Core biopsies will be obtained. Refer to the Biospecimen Sampling Manual for details including processing of fresh tissue (e.g. in media, RNAlater) where relevant.

The first progression (PSA or radiological) biopsy will be guided by molecular imaging at first progression (⁶⁸Ga-PSMA PET/CT and ¹⁸F-FDG PET) and will target sites of metabolic tumour progression (these sites may be PSMA avid or FDG avid, but not negative on both PET images, unless a site of clear progression and tumour involvement by RECIST criteria on the diagnostic CT scan). Refer to the Biospecimen Sampling Manual for details including processing of fresh tissue (e.g. in media, RNAlater) where relevant.

6.2.5 Aspects of health-related quality of life

McGill-Melzack Present Pain Intensity Scale, the EORTC QLQ-C30 and Patient Disease and Treatment Assessment Form will be completed every 4-6 weeks until radiographic progression (see schedule of assessments). The Fear of cancer progression short form will be completed at baseline only.

6.2.6 Health resource use

Information on health care resource use will be collected via three avenues. (1) Data on outpatient use of medical and pharmaceutical services will be collected by asking patients to consent to access their Medicare records held by services Department of Human Services. This will provide access to data on outpatient medical, diagnostic and pathology services via the Medical Benefits Schedule (MBS) and outpatient medications via the Pharmaceutical Benefits Scheme (PBS). A copy of the consent form is provided. (2) Data on inpatient services (hospitalisations) will be collected via standard CRF to be completed by trial staff. (3) Time, staff and equipment requirements for the delivery of Lu-PSMA will be recorded as part of the trial to provide an assessment of the resource implications of Lu-PSMA. This will be an important element of the resource use assessment of this trial.

6.2.7 Blood Collection

Local pathology laboratories will be used for routine blood tests. Blood will be taken Day 15, then 4 weekly (± 7 days) prior to the administration of treatment.

Blood will be collected for translational research (section 7.10). These will be collected locally at baseline, Day 92 and at first progression (PSA or radiographic progression whichever occurs first) with collection and management to be detailed in the Biospecimen Sampling Manual.

6.3 End of Treatment and 30 - 42 day Safety Assessment

An end of treatment and safety assessment should be performed 30 to 42 days, and 84 days after the last dose of study treatment to include any adverse events occurring within 12 weeks after the last dose of study treatment. In the event of unresolved toxicity participants should continue to be followed.

6.4 Follow-Up after Study Treatment Discontinuation

Study-specific follow-up assessments should be completed at the specified time points (± 7 days). Participants who stop study treatment prior to the time recommended in the protocol will continue follow-up visits according to the protocol.

If a participant wishes to stop the study visits, they will be requested to allow their ongoing health status to be periodically reviewed via phone contact or from their general practitioner, or medical records.

7 OUTCOMES, ENDPOINTS AND OTHER MEASUREMENTS

7.1 PSA Progression-Free Survival (PCWG3)

The primary endpoint of this study is PSA progression-free survival defined as the interval from the date of randomisation to the date of first evidence of PSA progression or the date of last known follow-up without PSA progression.

PSA progression is defined as a rise in PSA by more than or equal to 25% AND more than or equal to 2 ng/mL above the nadir (lowest PSA point). This needs to be confirmed by a repeat PSA performed at least 3 weeks later.

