4.2 Inclusion Criteria

1. Males aged 18 or older with metastatic adenocarcinoma of the prostate defined by:
 - Documented histopathology of prostate adenocarcinoma (no features of neuroendocrine carcinoma)
 - OR
 - Metastatic disease typical of prostate cancer
2. Castration-resistant prostate cancer (defined as disease progressing despite castration by orchectomy or ongoing luteinising hormone-releasing hormone agonist or antagonist).
3. Progressive disease with rising PSA defined by PCWG3 criteria (sequence of 2 rising values at a minimum of 1-week intervals) AND $\text{PSA} \geq 5 \text{ ng/mL}$.
4. At least 2 of the following risk factors for early treatment failure with enzalutamide:
 - i. $\text{LDH} \geq \text{ULN}$
 - ii. $\text{ALP} \geq \text{ULN}$
 - iii. $\text{Albumin} < 35 \text{ g/L}$
 - iv. De novo metastatic disease (M1) at initial diagnosis *
 - v. < 3 years since initial diagnosis
 - vi. > 5 bone metastases *
 - vii. Visceral metastases *
 - viii. PSA doubling time < 84 days
 - ix. Pain requiring opiates for > 14 days
 - x. Prior treatment with abiraterone
- * Based on conventional imaging (CT and/or bone scan)
5. Target or non-target lesions according to RECIST 1.1 (Appendix 1) or PCWG3 (Appendix 3)
6. Significant PSMA avidity on ^{68}Ga -PSMA PET/CT, defined as $\text{SUV}_{\text{max}} > 15$ at a single site (regardless of lesion size) and $\text{SUV}_{\text{max}} > 10$ at sites of disease $\geq 10\text{mm}$ (unless subject to factors explaining a lower uptake, e.g. respiratory motion, reconstruction artefact)
7. ECOG performance status 0-2 (Appendix 2)
8. Adequate renal function:
 - Creatinine clearance $\geq 40\text{mL/ min}$

9. Adequate liver function:
 - Bilirubin < 1.5 x upper limit of normal (ULN) (or if bilirubin is between 1.5 - 2x ULN, must have a normal conjugated bilirubin)
 - AST or ALT ≤ 2.0 x ULN (or ≤ 5.0 x ULN in the presence of liver metastases)
10. Adequate bone marrow function:
 - Platelets ≥ 100 x10⁹/L
 - Haemoglobin ≥ 90g/L (no red blood cell transfusion in last 4 weeks)
 - Neutrophils > 1.5 x10⁹/L
11. Estimated life expectancy > 12 weeks
12. Study treatment both planned and able to start within 21 days of randomisation
13. Willing and able to comply with all study requirements (including both treatments: enzalutamide and Lu-PSMA), and all required study assessments
14. Signed, written, informed consent

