7.2 Radiographic Progression-Free Survival (PCWG3 / RECIST 1.1)

Radiographic progression-free survival is defined as the interval from the date of randomisation to the date of first evidence of radiographic progression on imaging (PCWG3 criteria for bone lesions, see Appendix 3 and RECIST 1.1 for soft tissue lesions, see Appendix 1), or the date of last known follow-up without progression.

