7.5 Clinical progression-free survival

Clinical progression free survival (PFS) is defined as the interval from the date of randomisation to the date of first clinical evidence of disease progression or death from any cause, whichever occurs first, or the date of last known follow-up without clinical progression.

Clinical progression is defined by progression on imaging (PCWG3 criteria for bone lesions and RECIST 1.1 for soft tissue lesions; see Appendix 1 & 3), development of symptoms attributable to cancer progression, the need for radiotherapy to new metastases or initiation of other anticancer treatment for prostate cancer.

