16.3 Appendix 3: Prostate Cancer Working Group 3 (PCWG3) Criteria

The sections that apply to this trial are the criteria for PSA response and progression, and the criteria for bone lesion “prevent/delay end points (progression).

Variable	PCWG3 (2016)
PSA	
 - Recognize that a favorable effect on PSA may be delayed for 12 weeks or more, even for a cytotoxic drug - Monitor PSA by cycle but plan to continue through early rises for a minimum of 12 weeks unless other evidence of progression - Ignore early rises (prior to 12 weeks) in determining PSA response 
For control/relieve/eliminate endpoints:
 
 - Describe absolute changes in PSA over time from baseline to best response 
For delay/prevent endpoints:
 
Decline from baseline:
 
 - Record time from start of therapy to first PSA increase that is $\geq 25\%$ and ≥ 2 ng/mL above the nadir, and which is confirmed by a second value 3 or more weeks later (ie, a confirmed rising trend) 
No decline from baseline:
 
 - PSA progression $\geq 25\%$ and ≥ 2 ng/mL after 12 weeks

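### PSA and radiographic PFS as defined in 7.1 and 7.2 leave out death, so the primary endpoint is time to PSA progression under a PFS label, and the 150-event trigger may be out of reach

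*Protocol*

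**What the plan says.** - **Protocol 7.1 (primary endpoint).** Time runs from randomisation to "the date of first evidence of PSA progression or the date of last known follow-up without PSA progression". Those are the only two outcomes.
- **Protocol 7.2 (radiographic PFS).** The event is "the date of first evidence of radiographic progression on imaging"; the alternative is "or the date of last known follow-up without progression". Death is again absent.
- **Protocol 7.5 (clinical PFS).** The event is "the date of first clinical evidence of disease progression or death from any cause, whichever occurs first".
- **Protocol 7.7.** Overall survival is a separate endpoint.
- **Protocol 16.3 (PCWG3 appendix).** For delay endpoints the PSA rule is "Record time from start of therapy to first PSA increase" meeting the size and confirmation criteria. It has no death component.
- **Protocol 13.1.** 160 men, 1:1, are recruited over 12 months and followed to 150 events, about 18 months more. This gives 80% power at two-sided 5% for HR 0.625 with a control median PSA PFS of 5 months. The only allowance is for non-adherence in up to 2 participants.
- **Protocol 13.2.** PSA PFS is compared by log-rank test and Cox regression, with Kaplan-Meier curves. A later SAP is to add detail on these methods.

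**The concern.** An endpoint named progression-free survival is normally read as alive and free of progression. Under 7.1 a man who dies before PSA progression contributes only a last follow-up date, so he leaves the risk set in the same way as a man who is well at data cut-off. The protocol does not use the word censored for him, but the two-limb definition permits nothing else. Section 7.5 shows that the protocol names death when it means to count it, and no other section restores death to 7.1 or 7.2. A SAP that counted death would contradict 7.1 rather than fill a gap.

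Two things are at stake. First, interpretation: the experimental arm adds a radioligand, and an excess of deaths before PSA progression on that arm would not count against it in the primary result. The Kaplan-Meier, log-rank and Cox analyses also assume independent censoring, which is doubtful when men are selected for early treatment failure. Second, feasibility: the analysis waits for 150 of 160 men to have an event, and every death before PSA progression removes one possible event.

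**Working it through.** **Inputs.** From Protocol 13.1: 80 men per arm, control median 5 months, HR 0.625, accrual R = 12 months, analysis at about T = 30 months. With exponential times the control PSA hazard is ln 2/5 = 0.1386 per month and the combination hazard is 0.625 × 0.1386 = 0.0866. The hazard d of death before PSA progression is not in the protocol. I assume 1% and 2% per month, equal in both arms unless stated.

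**1. The planned 150 events.**
- Schoenfeld: 4(1.960 + 0.842)²/(ln 0.625)² = 142.1, so 143.
- Freedman: (1.960 + 0.842)² × (1.625/0.375)² = 147.4, so 148.
- Diluting for 2 of 80 non-adherent men (HR about 0.632 to 0.634), Schoenfeld gives 150 to 152.

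The planned number reproduces; the sample-size arithmetic is not at fault.

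**2. The planned timing, with no deaths.** The probability of an event by T is 1 − [exp(−λ(T−R)) − exp(−λT)]/(λR).
- Month 30: 80 × 0.960 + 80 × 0.869 = 76.8 + 69.5 = 146.3 events.
- Month 36: about 152 events.

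The stated follow-up is therefore roughly right, but only if nobody dies or is lost before PSA progression.

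**3. The most PSA-only events that could ever occur.** With deaths censored, the ceiling is 80 × [0.1386/(0.1386 + d) + 0.0866/(0.0866 + d)].
- d = 0.01: 74.6 + 71.7 = 146.3.
- d = 0.02: 69.9 + 65.0 = 134.9.
- d = 0.0073 (5% of control first events are deaths, since 0.1386 × 0.05/0.95 = 0.0073): 149.8.

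So 150 is out of reach, however long the follow-up, once the death hazard is about 0.7% per month. That the 1% ceiling equals the month-30 count in step 2 is a coincidence.

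**4. Month 30, current definition against the composite.** The composite HR is (0.0866 + d)/(0.1386 + d). Power is Φ(√D/2 × |ln HR| − 1.960), with D the number of events.

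| d per month | PSA-only events | Deaths censored | Composite events | Power as written (HR 0.625) | Composite HR | Composite power |
|---|---|---|---|---|---|---|
| 1% | 136 | 13 | 149 | 78% | 0.650 | 75% |
| 2% | 128 | 24 | 151 | 76% | 0.672 | 69% |

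If HR 0.625 does apply to the composite, 149 events give about 82% power.

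**5. An excess of deaths on Lu-PSMA.** With 1% per month in control and 1.5% on the combination, the composite HR is (0.0866 + 0.015)/(0.1386 + 0.01) = 0.684. The HR for PSA progression alone is still 0.625, so the primary result does not register the excess.

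**The case against.** The best defence is that 7.1 follows the criteria it cites. The PCWG3 appendix describes time to a confirmed PSA rise without death, the rule in 7.1 is openly stated, and time to PSA progression is a legitimate activity endpoint in phase 2. That stands, but it defends a different name: if this is what is meant, the PFS label is wrong in 7.1 and wherever it is repeated, including the objectives and the sample-size section.

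Nor are deaths hidden from the trial. They count in clinical PFS and overall survival, fatal events are SAEs, and the safety committee monitors key safety endpoints. This is correct, and limits the complaint to the primary result and radiographic PFS.

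Three stronger readings are tempting and are not supported:

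- **That bias has been demonstrated.** The calculation above assumes independent hazards, under which censoring deaths does not bias the HR for PSA progression. The gap between 0.625 and 0.650 or 0.684 is a difference between two estimands. Informative censoring is plausible, but nothing in the protocol lets one size it. The eligibility requirement "Estimated life expectancy > 12 weeks" is a floor, not a death rate.
- **That the current wording costs power compared with counting death.** At 1% per month with equal hazards, power goes from about 78% to about 75% when death is added, because unaffected deaths pull the HR toward 1.
- **That starting new anticancer treatment should also be a primary event because 7.5 counts it.** Section 7.1 follows men through a switch and does not censor them there, which fits the intention-to-treat principle in 13.2. In an open-label trial, such an event would bring an investigator's decision into a laboratory-based endpoint, and clinical PFS already contains it.

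**Conclusion.** The point holds on the wording alone: 7.1 and 7.2 define time to PSA and time to radiographic progression but call them progression-free survival, and they differ from 7.5 on death. Deaths before progression therefore do not count in the primary result. Whether the censoring is informative, and by how much, cannot be settled from the protocol.

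The consequence for the event trigger depends on an assumed rate. With constant hazards and the planning values of 13.1, the ceiling on PSA-only events is about 146 at 1% per month and about 135 at 2%, against 150 required. Below roughly 0.7% per month the target remains attainable in principle, though later than planned. Loss to follow-up would lower the ceiling further and is not included.

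**What to change.** **Preferred.** Add death from any cause, whichever comes first, to the event definitions in 7.1 and 7.2, matching 7.5. Keep time to PSA progression with deaths censored as a sensitivity analysis. State in 13.1 whether the 5-month median and HR 0.625 refer to the composite, and restate power if they do not.

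**If PSA progression alone is intended.** Rename the two endpoints time to PSA progression and time to radiographic progression throughout, treat death as a competing event in the analysis, and recheck whether 150 events can be reached or set a trigger that can.

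**Cost.** Either route is a wording amendment, best made before data lock. Survival is already collected under the assessment schedule, so no new data are needed. The price of the preferred route is an endpoint less specific to PSA. If treatment does not affect these deaths, the HR also moves toward 1, for example to 0.650 with about 75% power at 1% per month.

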7.3 PSA response rate (PSA RR)

PSA response rate is defined as the proportion of participants in each group with a PSA reduction of $\geq 50\%$ from baseline.

Early rises in PSA prior to 12 weeks will be disregarded in determining PSA response (see Appendix 3 for more details on the PCWG3 criteria).

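### For men whose PSA never falls, Section 7.1 and Appendix 3 date the primary event about 1 to 3 months apart, and the protocol does not say which governs.

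*Protocol*

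**What the plan says.** Protocol Section 7.1 carries PCWG3 in its title and states that "The primary endpoint of this study is PSA progression-free survival". Progression there is "a rise in PSA by more than or equal to 25% AND more than or equal to 2 ng/mL above the nadir", and "This needs to be confirmed by a repeat PSA performed at least 3 weeks later". One rule covers everyone. If PSA never falls, the lowest value is the baseline value, so a confirmed early rise over baseline is an event.

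Appendix 3 (Section 16.3) opens with "The sections that apply to this trial are the criteria for PSA response and progression" and then gives two branches. After a decline, it uses the confirmed rise over nadir. Under the entry "No decline from baseline", the same size of rise counts only if it occurs "ng/mL after 12 weeks". It also instructs sites to "Monitor PSA by cycle but plan to continue through early rises for a minimum of 12 weeks unless other evidence of progression".

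Section 7.3 repeats the 12-week exclusion in the body of the protocol, but for response only: "Early rises in PSA prior to 12 weeks will be disregarded in determining PSA response". Section 7.1 has no counterpart for progression.

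Under Section 6.1, PSA is measured at Day 15 and then every 4 weeks. Note 1 to that schedule sends the reader to Section 7.1 for the definition of PSA progression.

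**The concern.** Two passages of the same document define the primary event, and for one group of participants they give different dates from the same PSA values. This is more than detail that can wait for the analysis plan, because both rules are already stated and nothing says which prevails.

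The trial is open-label (Section 3), and Section 13.2 requires the analysis plan only before data-lock. Left as it is, the choice could be made after PSA results by arm are visible. The affected events lie in the first 3 months of the curves, so the choice enters the log-rank test and the Cox estimate.

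The definition also has a use during the trial. Notes 1 and 5 to the schedule make first PSA or radiological progression the trigger for PSMA PET, FDG PET, translational bloods and an optional biopsy.

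**Working it through.** **The plan's own figures first.** Inputs from Section 13.1: HR 0.625, two-sided 5%, 80% power, 1:1 allocation, 160 participants, 150 events, control median 5 months, up to 2 non-adherent participants.

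- Freedman: (1.625/0.375)² × (1.960 + 0.842)² = 18.78 × 7.849 = 147.4, so 148 events.
- Schoenfeld: 4 × 7.849 / (ln 0.625)² = 31.40 / 0.2209 = 142.1, so 143 events. With the log hazard ratio diluted by 2/80, 31.40 / (0.4700 × 0.975)² = 149.5, so 150 events, and power at 150 events is 80.1%.
- With exponential medians of 5 and 5/0.625 = 8 months, 12 months of accrual and 18 more of follow-up, 146.3 events are expected.

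The stated design reproduces, and the conflict does not alter that calculation.

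**Dates under the two rules.** Scheduled PSA visits fall on Days 15, 43, 71 and 99. Twelve weeks is Day 84. The Day 71 visit with its 7-day window ends at Day 78, so the first scheduled PSA after 12 weeks is Day 99. For a participant with no decline whose rise persists:

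| Rise first seen | Section 7.1 | Appendix 3 | Difference |
|---|---|---|---|
| Day 15 | Day 15 | Day 99 | 84 days (2.8 months) |
| Day 43 | Day 43 | Day 99 | 56 days (1.8 months) |
| Day 71 | Day 71 | Day 99 | 28 days (0.9 months) |

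For a participant whose PSA first declines, both texts use the confirmed nadir rule and the difference is 0.

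**Average shift, as an illustration.** Assume an exponential curve with the 5-month control median, read at the scheduled visits (Day 71 = 2.33 months). The shares first detected at Days 15, 43 and 71 are 6.6%, 11.2% and 9.9%, together 27.6%. If all of these were no-decline events, the mean shift would be (6.6 × 84 + 11.2 × 56 + 9.9 × 28) / 27.6 = about 53 days, or 1.7 months.

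**Number exposed.** The protocol does not say how many participants will have no PSA decline. Its Synopsis gives 25% primary resistance among men starting enzalutamide. As a proxy, 0.25 × 160 = 40. This is an assumption, because resistance is not defined there as absence of decline.

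**How early a qualifying rise can occur.** The time to a given relative rise is doubling time × log2(ratio). At a doubling time of 84 days, the bound of one risk factor in Section 4.2, a 25% rise takes 84 × 0.322 = 27 days. The 2 ng/mL condition must be met as well. At the eligibility floor of 5 ng/mL the required rise is 2/5 = 40%, which takes 84 × 0.485 = 40.8 days. A 25% rise within the 14 days to Day 15 needs a doubling time of 14/0.322 = about 43 days or less. The 84-day difference is therefore the extreme case.

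**Medians.** Moving 5% to 25% of participants per arm from their early visit to Day 99 in an exponential illustration left both medians unchanged, because both lie beyond Day 99. Only the early part of the curves moves.

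**The case against.** The best defence is that Section 7.1 is self-contained and governs. It is the endpoint section, note 1 to the schedule points to it, and unlike Sections 7.2 and 7.3 it does not refer to an appendix. Appendix 3 largely reproduces generic criteria, and even times progression from start of therapy where Section 7.1 times it from randomisation. This has weight, and it means that events under Section 7.1 cannot simply be called wrong. It does not settle the matter. Section 7.1 and the primary objective both carry the PCWG3 label, and the opening sentence of Appendix 3 applies its PSA progression criteria to this trial without exception.

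Two of the supporting passages are weaker than they look. The advice to continue through early rises can be read as guidance on monitoring and treatment, consistent with Section 5.7, where PSA progression alone does not require stopping. The 12-week clause in Section 7.3 concerns response, a different endpoint. The contradiction rests on the no-decline branch.

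A reader might infer that Section 7.1 penalises the experimental arm by counting events before Lu-PSMA, first given on Day 15, can act. The documents do not support this. A Day 15 rise must be confirmed at least 3 weeks later, in practice at Day 43, which is 28 days after the first dose. A rise that has reversed by then is no event. A bias would need an assumed delay in PSA effect and an assumed proportion of non-responders rescued. The protocol gives neither, and the sign of the change in hazard ratio depends on the delay chosen.

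**Conclusion.** The contradiction stands and concerns the primary endpoint, but it is confined to participants whose PSA does not decline from baseline. For them the event date differs by 28, 56 or 84 days, assuming that visits are on schedule and the rise persists to Day 99. An early rise that was confirmed and later reversed would be an event under Section 7.1 and not at Day 99 under Appendix 3, so the gap could then be longer.

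The figure of 40 of 160 rests on the resistance proxy alone. It would be an overstatement to say that primary event dates in general differ by 2 to 3 months, that the hazard ratio is biased in a known direction, or that the sample size is inadequate.

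**What to change.** Write both branches into Section 7.1, before outcomes are seen:

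- after a PSA decline, the present confirmed nadir rule;
- with no decline, a rise over baseline of at least 25% and at least 2 ng/mL at or after week 12, earlier rises being disregarded.

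Keep confirmation at least 3 weeks later in both branches. Appendix 3 states it only for the decline branch, and copying that text unchanged would let a single value become a primary event. State whether the 12 weeks run from randomisation or from start of therapy. Report the present Section 7.1 wording as a sensitivity analysis.

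No new PSA measurements are needed. There are two costs. Events in participants with no decline are dated later. Notes 1 and 5 to the schedule must also say which definition triggers the progression PET scans, translational bloods and optional biopsy, since those procedures now follow the Section 7.1 definition.
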